---

## LIST OF ABBREVIATIONS

ADE	adverse device effect
AE	adverse event
bimekizumab-AI-1mL	1mL bimekizumab auto-injector
bimekizumab-AI-2mL	2mL bimekizumab auto-injector
bimekizumab-SS-1mL	1mL bimekizumab safety syringe
bimekizumab-SS-2mL	2mL bimekizumab safety syringe
BKZ	bimekizumab
BMI	body mass index
COVID-19	Coronavirus Disease 2019
ES	Enrolled Set
FAS	Full Analysis Set
FAS-a	Full Analysis Set for the bimekizumab-AI-1mL Full Analysis Set for the bimekizumab AI 2mL
FAS-s	Full Analysis Set for the bimekizumab-SS-1mL Full Analysis Set for the bimekizumab SS 2mL
HLT	higher level term
IFU	instructions for use
IMP	investigational medicinal product
LLOQ	lower level of quantification
MedDRA	Medical Dictionary for Regulatory Activities
PFS	prefilled syringe
PK	pharmacokinetic(s)
PK-PPS	Pharmacokinetic Per Protocol Set

---

PK-PPS-a	Pharmacokinetic Per Protocol Set for the bimekizumab-AI-1mL Pharmacokinetic Per Protocol Set for the bimekizumab-AI-2mL
PK-PPS-s	Pharmacokinetic Per Protocol Set for the bimekizumab-SS-1mL Pharmacokinetic Per Protocol Set for the bimekizumab-SS-2mL
PEOT	Premature End of Treatment
PSO	psoriasis
PT	preferred term
Q4W	every 4 weeks
Q8W	every 8 weeks
SADE	serious adverse device effect
SAE	serious adverse event
SAP	Statistical Analysis Plan
sc	subcutaneously
SIAQ	Self-Injection Assessment Questionnaire
SD	standard deviation
SFU	Safety Follow-Up
SOC	System Organ Class
SS	Safety Set
SS-a	Safety Set for the bimekizumab-AI-1mL Safety Set for the bimekizumab AI 2mL
SS-s	Safety Set for the bimekizumab-SS-1mL Safety Set for the bimekizumab SS 2mL
TEADE	treatment-emergent adverse device effect
TEAE	treatment-emergent adverse event

VAS visual analog scale

WHO World Health Organization

PUBLIC COPY

This document cannot be used to support any marketing authorization application and any extensions or variations thereof.

## 1 INTRODUCTION

This statistical analysis plan (SAP) defines the scope of the statistical analyses and provides a detailed description of the statistical methodology for subject data obtained in this substudy of PS0014. The SAP is based on the following study document:

- Final Protocol DV0002, 26 Jul 2018.
- Protocol amendment 1, 28 Oct 2019.

All references to study protocol hereafter refer to this version of the protocol.

All analyses will be performed separately for the 1mL device cohort and for the 2mL device cohort. Once subjects in the 1mL device cohort complete DV0002, a final analysis will be performed for that cohort, and a clinical study report will be prepared. A separate final analysis will be performed for the 2mL device cohort once all data have been collected and will be reported separately from the initial clinical study report.

## 2 PROTOCOL SUMMARY

### 2.1 Study objectives

#### 2.1.1 Primary objective

The primary objective of the study is to evaluate for each device the ability of subjects with moderate to severe chronic plaque psoriasis (PSO) to safely and effectively self-inject bimekizumab 8 weeks after training in the self-injection technique.

#### 2.1.2 Secondary objective

The secondary objective of the study is to evaluate, for each device, the ability of subjects with moderate to severe chronic plaque PSO to safely and effectively self-inject bimekizumab immediately after training in the self-injection technique.

#### 2.1.3 Other objectives

Other objectives of the study are to evaluate the following:

- Subject experience of self-injection using the investigational devices as assessed by the pain visual analog scale (VAS) and the Self-injection Assessment Questionnaire (SIAQ).
- Trough pharmacokinetic (PK) (trough bimekizumab) levels associated with self-injection using the investigational devices, injection by study personnel, injection site (abdomen or thigh), and body mass index (BMI) category (by tertile).
- The structural and mechanical integrity of the investigational devices after completion of self-injection.
- The overall safety and tolerability of self-injections using the investigational devices.

### 2.2 Study variables

#### 2.2.1 Primary outcome variable

The primary outcome variable is the percentage of subjects able to self-administer safe and effective injections using the 1mL bimekizumab safety syringe (bimekizumab-SS-1mL), 1mL bimekizumab auto-injector (bimekizumab-AI-1mL), 2mL bimekizumab safety syringe

(bimekizumab SS 2mL), or 2mL bimekizumab auto-injector (bimekizumab-AI-2mL), 8 weeks after training in self-injection technique. Safe and effective self-injection will be evaluated by the study personnel and is defined as:

- Complete dose delivery: Subject self-injects the complete dose of bimekizumab as confirmed by a visual inspection of the device which shows that the investigational medicinal product (IMP) is delivered completely (ie, container is empty), and
- No adverse device effects (ADEs) that would preclude continued use of the device for self-injection (ie, no serious adverse device effects (SADEs) and/or ADEs leading to withdrawal from the DV0002 substudy).

In the DV0002 substudy, for the 1mL devices the 320mg bimekizumab dose will be administered as two 160mg injections with either 2 bimekizumab-SS-1mL devices or 2 bimekizumab-AI-1mL devices. Each self-injection will be evaluated for safety and effectiveness by study personnel using the above criteria. The endpoint of safe and effective self-injection will be met only if both self-injections are determined to be safe and effective.

For the 2ml devices, the 320mg bimekizumab dose will be administered as 1 injection with either 1 bimekizumab-SS-2mL or 1 bimekizumab-AI-2mL device. Each self-injection will be evaluated for safety and effectiveness by study personnel using the above criteria. The endpoint of safe and effective self-injection will be met if the single self-injection is determined to be safe and effective.

### **2.2.2 Secondary outcome variable**

The secondary outcome variable is the percentage of subjects able to self-administer safe and effective injections using the bimekizumab-SS-1mL, bimekizumab-AI-1mL bimekizumab SS 2mL, or 1 bimekizumab-AI-2mL at DV0002 Baseline (the first self-injection visit, immediately after training in self-injection technique). Safe and effective self-injection will be evaluated by study personnel and is defined as for the primary outcome variable (see Section 2.2.1).

### **2.2.3 Other variables**

#### **2.2.3.1 Outcome variables**

The other outcome variables are:

- Responses to pre-injection SIAQ (versions 2.0 and 2.1) at DV0002 Baseline.  
Whenever SIAQ is assessed, version 2.0 of the SIAQ will be used to assess bimekizumab-SS-1mL and bimekizumab-SS-2mL and version 2.1 of the SIAQ will be used to assess bimekizumab-AI-1mL and bimekizumab AI 2mL.
- Responses to post-injection SIAQ (versions 2.0 for bimekizumab-SS-1ml and 2.1 for bimekizumab-1ml-AI) by visit following self-injection using the assigned device at DV0002 Baseline and Week 8.
- Injection site pain (using a VAS; 100mm) by visit after self-injection using the assigned device at DV0002 Baseline and Week 8.

- Percentage of used devices identified as having structural or mechanical integrity issues after completion of self-injection. This is based on a visual examination of the device that shows clear evidence of damage and/or compromised structural or mechanical integrity.

### **2.2.3.2 Pharmacokinetic variable**

The PK variable is trough PK (bimekizumab) levels associated with self-injection using the investigational device, injection by study personnel, injection site (abdomen or thigh), and BMI category (by tertile). Trough levels will be assessed at DV0002 Baseline, Week 4, Week 8, and Week 12 for subjects who receive bimekizumab Q4W and trough levels will be assessed at DV0002 Baseline, Week 8, and Week 16 for subjects who receive bimekizumab Q8W.

### **2.2.3.3 Safety variable**

The other safety variable is the occurrence of ADEs. An ADE is an adverse event (AE) related to the use of an investigational device. An ADE must meet 1 or more of the following criteria:

- Adverse event resulting from insufficiencies or inadequacies in the instructions for use (IFU), the deployment, the implantation, the installation, the operation, or any malfunction of the investigational medical device.
- Adverse event that is a result of a use error or intentional misuse of the investigational device.

Additional safety and tolerability variables will be collected as described in the PS0014 study protocol.

## **2.3 Study design and conduct**

### **2.3.1 Study description**

DV0002 is a Phase 3 open-label, randomized, noncomparator, North America-only substudy to PS0014. PS0014 will evaluate the long-term safety, tolerability, and efficacy of bimekizumab in subjects with moderate to severe chronic plaque PSO; study personnel will administer bimekizumab to subjects in a 1mL PFS.

In the DV0002 substudy, the safe and effective use of the bimekizumab-SS-1mL, bimekizumab-AI-1mL, bimekizumab-SS-2mL, or the bimekizumab-AI-2mL for the sc self-injection of bimekizumab by subjects with PSO will be evaluated.

Subjects from selected sites in the PS0014 feeder studies PS0008, PS0009, and PS0013 will be eligible for the DV0002 substudy. At DV0002 Baseline, each subject will be provided with training in self-injection and will receive the IFU and any other applicable training materials.

For the 1mL device cohort, subjects in the DV0002 substudy will perform self-injections at DV0002 Baseline (corresponding to the Baseline Visit of PS0014) with a subsequent self-injection at DV0002 Week 8 (corresponding to Week 8 of PS0014).

To allow flexible enrollment, subjects may be randomized in the 2mL device cohort at the PS0014 Week 24, Week 28, or Week 32 visit for subjects receiving bimekizumab Q4W or the PS0014 Week 24 or Week 32 visit for subjects receiving bimekizumab Q8W.

For the 2mL device cohort, subjects will perform self-injections at DV0002 Baseline with a subsequent self-injection 8 weeks after training. The 2mL device cohort will evaluate 2 self-injection devices: the bimekizumab SS 2mL and the bimekizumab AI 2mL.

### **2.3.2 Treatment Period**

During the 16-week Treatment Period of DV0002, subjects will receive either bimekizumab 320mg Q8W or bimekizumab 320mg Q4W, based on their assigned dose at PS0014 Baseline. Baseline for DV0002 and Baseline for PS0014 will occur at the same time for the 1mL device cohort. In the 2mL device cohort, Baseline for DV0002 will occur at the PS0014 Week 24, Week 28, or Week 32 visit for subjects receiving bimekizumab Q4W or the PS0014 Week 24 or Week 32 visit for subjects receiving bimekizumab Q8W.

Eligible subjects (PS0014 entry criteria and DV0002 entry criteria) will be randomly assigned in a 1:1 ratio to perform self-injection using either the bimekizumab-SS-1mL or the bimekizumab-AI-1mL for the 1mL device cohort or using either the bimekizumab-SS-2mL or the bimekizumab-AI-2mL for the 2mL device cohort. Regardless of the assigned dose regimen, subjects will perform self-injection with the assigned device only at DV0002 Baseline and at DV0002 Week 8. For subjects in the bimekizumab 320mg Q4W dosing arm, injections will be administered by study personnel using the investigational device at Week 4 and Week 12; for subjects in both dosing arms, injections will be administered by study personnel using the investigational device at Week 16.

First treatment for the 1ml device cohort in PS0014 will be the timepoint of first bimekizumab injection in DV0002. First treatment in DV0002 will be the timepoint of first self-injection in DV0002.

After Week 16 in the DV0002 substudy, subjects will continue in PS0014.

### **2.3.3 Safety Follow-Up**

A device Safety Follow-up (SFU) telephone call will occur 1 week after the last self-administration (at DV0002 Week 9).

Subjects who are withdrawn from DV0002 but continue their PS0014 study participation will be required to perform an SFU telephone call 1 week after their final DV0002 dosing visit.

### **2.3.4 Withdrawal**

Subjects who are withdrawn from bimekizumab treatment (PS0014 study) during the course of DV0002 will also be required to follow the PS0014 withdrawal procedures that means subjects will undergo the Premature End of Treatment (PEOT) Visit assessments and will enter the SFU Period.

### **2.3.5 Study duration per subject**

The maximum DV0002 substudy duration will be 16 weeks for each subject. Subjects will then continue to receive treatment in PS0014 for the duration of the PS0014 study.

The end of the DV0002 substudy is defined as the date on which the last subject completes his/her DV0002 Week 16 Visit or withdraws from the study.

### 2.3.6 Planned number of subjects

For evaluation of the 1mL device, it is planned to enroll approximately 200 subjects; each device arm (bimekizumab-SS-1mL, bimekizumab-AI-1mL) will consist of approximately 100 subjects.

Once the 1mL device cohort has finished enrolling, the 2mL device cohort will start enrolling. For evaluation of the 2mL device, it is planned to enroll approximately 100 subjects; each device arm (bimekizumab SS 2mL or bimekizumab-AI-2mL) will consist of approximately 50 subjects.

It is anticipated that this study will involve up to 80 sites in North America.

## 2.4 Determination of sample size

This study will not be powered with respect to any endpoint and sample size is based on practical considerations.

### 1mL Device Cohort

For the 1mL device cohort, to maintain blinding in the PS0014 feeder studies, DV0002 will recruit subjects who were administered bimekizumab 320mg (Q4W or Q8W) and subjects who were administered placebo or ustekinumab in the PS0014 feeder studies. A total of 100 subjects (50 subjects per device arm) are planned for PK trough level analyses, but these analyses can only be performed on subjects who do not change their bimekizumab dose or dosing regimen (ie, 320mg bimekizumab Q4W or Q8W) between the PS0014 feeder studies and the DV0002 substudy. The DV0002 substudy will therefore enroll approximately 200 subjects (to compensate for subjects with bimekizumab dose changes) to ensure that 100 subjects are available for PK trough analysis.

Subjects who enroll in the DV0002 substudy 1mL device cohort will be randomly assigned to the bimekizumab SS 1mL or the bimekizumab AI 1mL device arms (each device arm will consist of approximately 100 subjects). Within each device arm, subjects will be divided into tertiles by BMI; there will be approximately 33 subjects per tertile, which is expected to yield approximately 16 to 17 subjects per tertile who are evaluable for steady state trough PK level analyses.

Subjects are evaluable for steady state trough PK level analyses, if they enter PS0014 on the same drug and dose as completing the feeder study and if they receive the drug at least 16-20 weeks before PS0014. The second condition is automatically fulfilled. Each subject in the feeder study will receive more than 20 weeks of the same treatment in the maintenance phase except escape subjects from PS0013 which are excluded from DV0002 enrollment.

### 2mL Device Cohort

Once the 1mL device cohort has finished enrolling, the 2mL device cohort will start enrolling. Subjects who participated in the 1mL device cohort of DV0002 are not eligible to enroll in the 2mL device cohort. For evaluation of the 2mL device, it is planned to enroll approximately 100 subjects. Subjects are evaluable for steady state trough PK level analysis if they receive the same bimekizumab administration (frequency and dose) from beginning of PS0014 through to the end of the sub-study. It is expected that most subjects will be evaluable for the PK trough level analyses.

Subjects who enroll in the DV0002 substudy 2mL device cohort will be randomly assigned to the bimekizumab-SS-2mL or the bimekizumab-AI-2mL device arms (each device arm will

consist of approximately 50 subjects). Within each device arm, subjects will be divided into tertiles by BMI; there will be approximately 16 to 17 subjects per tertile who are evaluable for steady state trough PK level analyses.

### 3 DATA ANALYSIS CONSIDERATIONS

#### 3.1 General presentation of summaries and analyses

Statistical analysis and generation of tables, figures, subject data listings, and statistical output will be performed using SAS Version 9.3 or higher. All tables and listings will use Courier New font size 9.

Descriptive statistics will be displayed to provide an overview of the study results. For continuous variables, descriptive statistics will include number of subjects with available measurements (n), mean, standard deviation (SD), median, minimum, and maximum.

For categorical variables, the number and proportion of subjects, will be presented. In addition, for the primary, secondary and other variables the 90% confidence interval (CI) based on the Exact Binomial, will also be presented. Unless otherwise noted, the denominator for percentages should be based on the number of subjects included in the respective analysis set. Subjects with missing data can generally be accounted for using either of the following approaches:

- For summaries of demographics and Baseline characteristics: summarize percentages based on all subjects in the analysis set and include a “Missing” category (corresponding to subjects with missing data for the variable being summarized) as the last row in the list of categories being summarized.
- For summaries of outcome and safety variables, unless otherwise specified: percentages will be summarized based only on those subjects with observed data for the variable being summarized. As the denominator may be different from the number of subjects in the analysis set being considered, the denominator should be displayed in the table. The general format for displaying this will be “n/NSub (%)”

Percentages will be presented to 1 decimal place. If the percentage is 100 or 0, no decimal will be presented. Typically, the % sign should be presented in the column header, but not with each individual value.

For bimekizumab PK concentrations, summary statistics will include geometric mean, geometric coefficient of variation (CV), 95% confidence intervals for geometric mean, arithmetic mean, SD, median, minimum, and maximum. All summaries of PK variables will be based on the observed values. No imputation will be used.

Decimal places for descriptive statistics will always apply the following rules:

- “n” will be an integer
- Mean, SD, and median will use one additional decimal place compared to the original data
- CV [%] will be presented with one decimal place
- Minimum and maximum will have the same number of decimal places as the original value.

Derived variables in general will display the mean, SD, and median to 1 more decimal place than the variables used in the derivation. If the number of decimal places reported in the raw data is

varied, then use either the maximum raw number of reported decimal places or 3, whichever is the lowest, as a guide for the descriptive statistics.

A complete set of data listings containing all documented data as well as calculated data will be generated

### 3.2 Analysis Time Points

If the early withdrawal visit occurs at a scheduled visit as outlined in the schedule of assessments, then no mapping is necessary, and any early withdrawal assessments should correspond to that scheduled visit. Premature study withdrawal visit assessments that occur on a date after a scheduled visit will be assigned to the next scheduled site visit per the protocol following the last visit where assessments were available.

### 3.3 Definition of Baseline values

The Baseline value is defined as the last non-missing measurement prior to the first self-injection at Visit 1 (Baseline).

If a scheduled Baseline assessment is taken on the same day as the first administration of study medication, then the assessment will be assumed to have been performed prior to study medication.

### 3.4 Relative Day

The relative day will be included in different listings and will be calculated as follows:

- If the start (stop) date occurred on or after the first dose in DV0002, but prior to the drug stop date, relative day is calculated as start (stop) date minus first dose date + 1
- If the start (stop) date occurred after the last dose of bimekizumab, the relative day to the most recent dose is calculated as start (stop) date minus most recent dose date. The relative day in this situation should be preceded by a '+'
- If the start (stop) date occurred before the first dose in DV0002, the relative day is calculated as start (stop) date minus first dose date. The relative day in this situation should be preceded by a '-'.

Relative day will only be computed for fully completed dates and will be missing for partial dates.

### 3.5 Protocol deviations

Important protocol deviations are deviations from the protocol which could potentially have a meaningful impact on the primary objective of the study. The criteria for identifying important protocol deviations and the classification of important protocol deviations will be defined within the project Data Cleaning Plan.

WHO declared a global COVID-19 pandemic on 11 March 2020. All subjects were recruited into this study during the pandemic and therefore the impact of COVID-19 on the study will be assessed. Deviations related to the Coronavirus Disease 2019 (COVID-19) global pandemic are unavoidable deviations from the protocol due to confirmed COVID-19 infection, suspected COVID-19 infection, general circumstances around COVID-19 without infection or any other deviation from the protocol due to COVID-19. COVID-19 protocol deviations will be reviewed

as part of the ongoing data cleaning process. Any COVID-19 impact protocol deviations that are determined to be important or not-important will be included in this summary. A by-subject listing of COVID-19 related protocol deviations will be provided.

### **3.6 Analysis sets**

#### **3.6.1 1mL Device Cohort**

##### **3.6.1.1 Enrolled Set**

The Enrolled Set (ES) will consist of all subjects who have given informed consent for DV0002.

##### **3.6.1.2 Safety Set**

Two different Safety Sets (SS) will be generated (1 for each device type): the bimekizumab-SS-1mL Safety Set (SS-s) and the bimekizumab-AI-1mL Safety Set (SS-a). Each SS will consist of all subjects in the study who receive at least 1 dose of bimekizumab by the indicated self-injection investigational device. Safety variables will be analyzed using the SS-s and SS-a.

##### **3.6.1.3 Full Analysis Set**

Two different Full Analysis Sets (FASs) will be generated (1 for each device type): FAS-s and FAS-a. Each FAS will consist of all subjects in the SS-s or SS-a who self-inject at least 1 dose of bimekizumab using the given device and who have an assessment of self-injection. All self-injection related endpoints will be analyzed using the FAS-s and FAS-a.

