3.2 Secondary objective

The secondary objective of the study is to evaluate, for each device, the ability of subjects with moderate to severe chronic plaque PSO to safely and effectively self-inject bimekizumab immediately after training in self-injection technique using the devices.

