4 STUDY VARIABLES

4.1 Outcome variables

4.1.1 Primary outcome variable

The primary outcome variable is the percentage of subjects able to self-administer safe and effective injections using the bimekizumab-SS-1mL, bimekizumab-AI-1mL, bimekizumab-SS-2mL, or bimekizumab-AI-2mL, 8 weeks after training in self-injection technique. Safe and effective self-injection will be evaluated by the study personnel and is defined as:

- Complete dose delivery: Subject self-injects the complete dose of bimekizumab as confirmed by a visual inspection of the device which shows that the IMP is delivered completely (ie, container is empty), and
- No ADEs that would preclude continued use of the device for self-injection (ie, no SADEs and/or ADEs leading to withdrawal from the DV0002 substudy).

In the DV0002 substudy, for the 1mL devices, the 320mg bimekizumab dose will be administered as two 160mg injections with either 2 bimekizumab-SS-1mL devices or 2 bimekizumab-AI-1mL devices. Each self-injection will be evaluated for safety and effectiveness by study personnel using the above criteria. The endpoint of safe and effective self-injection will be met only if both self-injections are determined to be safe and effective.

For the 2mL devices, the 320mg bimekizumab dose will be administered as 1 injection with either 1 bimekizumab-SS-2mL or 1 bimekizumab-AI-2mL device. Each self-injection will be evaluated for safety and effectiveness by study personnel using the above criteria. The endpoint of safe and effective self-injection will be met if the single self-injection is determined to be safe and effective.

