14.1 Definition of analysis sets

1mL Device Cohort

For the 1mL device cohort, 2 different Safety Sets (SS) will be generated (1 for each device type): the bimekizumab-SS-1mL Safety Set (SS-s) and the bimekizumab-AI-1mL Safety Set (SS-a). Each SS will consist of all subjects in the study who receive at least 1 dose of bimekizumab by the indicated self-injection investigational device. Safety variables will be analyzed using the SS-s and SS-a.

Two different Full Analysis Sets (FASs) will be generated (1 for each device type): the bimekizumab-SS-1mL Full Analysis Set (FAS-s) and the bimekizumab-AI-1mL Full Analysis Set (FAS-a). Each FAS will consist of all subjects in the SS-s or SS-a who self-inject at least 1 dose of bimekizumab using the given device and who have an assessment of self-injection. All self-injection related endpoints will be analyzed using the FAS-s and FAS-a.

For the PK analyses, 2 different Pharmacokinetic Per Protocol Sets (PK-PPS) will be generated (1 for each device type): the bimekizumab-SS-1mL PK-PPS (PK-PPS-s) and the bimekizumab-AI-1mL PK-PPS (PK-PPS-a). Each PK-PPS will consist of all subjects who receive the same bimekizumab administration (frequency and dose) in the PS0014 feeder studies as in the DV0002 substudy and who have at least 1 evaluable PK assessment in the DV0002 substudy without important protocol deviations that would affect the concentration. Pharmacokinetic variables will be analyzed using the PK-PPS-s and PK-PPS-a.

All PK assessments after baseline assessments from feeder study will be considered for the requirement of at least 1 evaluable PK assessment.

2mL Device Cohort

For the 2mL device cohort, the same analysis sets will be generated.

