### **11.1 Primary outcome**

The primary outcome variable is the percentage of all subjects able to self-administer safe and effective injections using the given device at DV0002 Week 8. Safe and effective self-injection will be evaluated by the study personnel as defined below:

- Complete dose delivery: Subject self-injects the complete dose of bimekizumab as confirmed by a visual inspection of the investigational device which shows that the IMP is delivered completely (ie, container is empty), and
- No ADEs that would preclude continued use of the device for self-injection (ie, no SADEs and/or ADEs leading to withdrawal from the DV0002 substudy).

All data to assess the primary outcome is collected on the subject self-injection of bimekizumab CRF page for DV0002 Week 8. For the number of subjects with safe and effective self-injections simply the cases which indicated “yes” for the question “Did the subject self-inject the complete dose of Bimekizumab” and “no” for the question “Where there any AEs related to use of the investigational device for self-injection” at Week 8 are counted.

For subjects in the 1mL device cohort, two self-injections will be performed at DV0002 Week 8 and the questions will be answered twice. If the answers are different between both self-injections in one visit, then the worst case of both answers will be used for analysis at this visit. Subjects with only one self-injection at one visit will be counted as non-responder. Assessments where the self-injection was not performed by the subject will be not included in any summary statistics.

The number and percentage of subjects with safe and effective self-injections will be tabulated separately for each device overall and within each device by dosing regimen. The 90% CIs based on the Exact Binomial method will be reported as well.

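### Full Analysis Set entry requires a self-injected dose, so a trained subject who attempts at Baseline, delivers nothing and stops is left out of the Baseline success percentage instead of counting as a failure

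*SAP*

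**What the plan says.** **Objective.** The secondary objective (Protocol 3.2) is whether subjects can "safely and effectively self-inject bimekizumab immediately after training in self-injection technique using the devices". The primary objective asks the same question 8 weeks after training.

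**FAS.** SAP 3.6.1.3, for the 1mL cohort: "Each FAS will consist of all subjects in the SS-s or SS-a who self-inject at least 1 dose of bimekizumab using the given device". It adds a second condition and the use of the set: subjects "who have an assessment of self-injection. All self-injection related endpoints will be analyzed using the FAS-s and FAS-a". SAP 3.6.2.3 repeats this for the 2mL cohort, and Protocol 14.1 admits subjects "who self-inject at least 1 dose of bimekizumab using the given device and who have an assessment of self-injection".

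**Safety Set.** SAP 3.6.1.2 (and 3.6.2.2 for 2mL) is worded differently: it admits subjects "who receive at least 1 dose of bimekizumab by the indicated self-injection investigational device". The dose must be received by the device; the text does not say self-injected.

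**Dose.** Neither document defines the word for set entry. For the 1mL devices, Protocol 4.1.1 says that "the 320mg bimekizumab dose will be administered as two 160mg injections with either 2 bimekizumab-SS-1mL devices or 2 bimekizumab-AI-1mL devices"; for the 2mL devices the 320mg dose is one injection. Protocol 7.1.2, however, calls one 1mL auto-injector a single-dose product.

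**Scoring.** Success needs complete delivery, both injections in the 1mL cohort, and no serious adverse device effect (ADE) or ADE leading to withdrawal. SAP 11.1 adds: "Subjects with only one self-injection at one visit will be counted as non-responder". It also drops assessments where someone other than the subject injected.

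**Denominators.** SAP 3.1 bases outcome and safety percentages on subjects with observed data. SAP 4.2 gives missing outcome data no special handling.

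**The concern.** The study estimates what share of trained subjects can use each device. The natural denominator at Baseline is the randomised, trained subjects who try. The FAS replaces it with a condition that arises after randomisation and is close to the endpoint itself. A subject who tries, delivers nothing and gives up is the clearest failure of the ability being measured, and that subject is removed from the denominator.

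The documents expect such events. Protocol 13.4 refers to malfunctions that cause failed or incomplete injections, and Protocol 6.3 provides for withdrawal by subjects who cannot or do not wish to go on self-injecting.

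The undefined word adds a second problem. If dose means the full 320mg, a 1mL subject who completes one of two injections and stops is also outside the FAS, as is a 2mL subject with partial delivery who stops. The non-responder rule in SAP 11.1 could then never reach that 1mL subject. Two programmers could build different sets from the same text.

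The study tests no hypothesis, so the percentage and its interval are the whole result. A one-directional exclusion acts directly on that result.

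**Working it through.** **Inputs.** Planned arm sizes from SAP 2.3.6: 200/2 = 100 per 1mL arm and 100/2 = 50 per 2mL arm. Interval: two-sided 90% exact binomial (SAP 11.1). The plan gives no power calculation and no expected success rate, so there is no further figure to reproduce. The number k of subjects who attempt at Baseline, deliver nothing and stop is an **assumption**, because the documents give no rate.

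**Direction.** With s successes among n subjects who attempt, the plan reports s/(n − k) and an attempt-based set reports s/n. Since n − k ≤ n, the plan's figure is equal or higher, never lower.

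**Interval.** When all x = n subjects succeed, the lower limit is 0.05^(1/n). Otherwise it is the 5% quantile of a Beta(x, n − x + 1) distribution. For example, 0.05^(1/49) = 94.1% and 0.05^(1/99) = 97.0%.

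**Baseline endpoint, all other subjects succeeding (lower 90% limit in brackets):**

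| Arm | k | As written | Attempt-based |
|---|---|---|---|
| 1mL, n = 100 | 0 | 100/100 = 100% (97.0%) | identical |
| 1mL | 1 | 99/99 = 100% (97.0%) | 99/100 = 99.0% (95.3%) |
| 1mL | 3 | 97/97 = 100% (97.0%) | 97/100 = 97.0% (92.4%) |
| 1mL | 5 | 95/95 = 100% (96.9%) | 95/100 = 95.0% (89.8%) |
| 2mL, n = 50 | 0 | 50/50 = 100% (94.2%) | identical |
| 2mL | 1 | 49/49 = 100% (94.1%) | 49/50 = 98.0% (90.9%) |
| 2mL | 3 | 47/47 = 100% (93.8%) | 47/50 = 94.0% (85.2%) |
| 2mL | 5 | 45/45 = 100% (93.6%) | 45/50 = 90.0% (80.1%) |

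The effect does not depend on perfect success elsewhere. In a 2mL arm with k = 1 and two other failures, 47/49 = 95.9% (87.7%) becomes 47/50 = 94.0% (85.2%).

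**Week 8.** A subject who stops after Baseline has no Week 8 observation. SAP 3.1 removes that subject from the Week 8 denominator whether or not the subject is in the FAS.

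**Safety tables.** SAP 10 runs the safety analyses on the Safety Sets. If one such subject received nothing by the device and had the only ADE in the arm, the table would show 0/49 instead of 1/50 = 2.0%, or 0/99 instead of 1/100 = 1.0%.

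**The case against.** Most of the opposing case limits the point, and much of it stands.

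- **A reader might infer that the FAS contains only subjects who have already succeeded.** The text does not support that. Entry needs a dose and an assessment, and the assessment may be negative. A subject with full delivery who then withdraws because of an ADE is in both sets and fails the protocol's endpoint.
- **A reader might infer that every incomplete delivery is excluded.** That holds only if dose means the full 320mg. The endpoint speaks separately of a complete dose, one 1mL auto-injector is called single-dose, and SAP 11.1 expects single-injection subjects inside the analysis. A wider reading reconciles these passages. The ambiguity is real; a firm contradiction is not established.
- **A reader might infer that the Safety Set has the same gate as the FAS.** It does not: a dose received by the device is enough, and partial delivery may qualify.
- **Such subjects and events stay visible elsewhere.** SAP 5.1 gives Enrolled Set disposition, discontinuation reasons and a listing of subjects excluded from analysis sets. ADEs go on the eCRF. Device deficiencies include use errors and are reportable even for an unused device (Protocol 11.1.1.3 and 11.1.2.2). This stands, but none of it puts the failure into the Baseline percentage.
- **The case may be rare.** Subjects must be willing to self-inject and judged able to use the device, and they are trained and observed. That bears on k, which may be zero. It does not justify the rule.

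**Conclusion.** The point holds in a narrow form. A randomised, trained subject who attempts at Baseline, delivers no drug and never self-injects is outside the FAS on any reading of the text, and outside the Safety Set if no dose was received by the device. Whether subjects with one of two 1mL injections, or partial 2mL delivery, who then stop are also outside depends on an undefined word.

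The bias runs one way and affects the secondary (Baseline) percentage. Each such subject is worth about 1 percentage point in a 1mL arm and 2 points in a 2mL arm when all others succeed. The first one moves the lower 90% limit by 97.0 − 95.3 = 1.7 points and 94.1 − 90.9 = 3.2 points respectively. These sizes rest on planned arm sizes and an assumed count; if no subject fits the description, the results are identical.

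A reader might infer that the primary Week 8 percentage is inflated by the same route. For a subject who stops after Baseline, FAS entry alone does not do this, because the observed-data rule already excludes that subject. The change is still worth making before analysis.

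**What to change.** In Protocol 14.1 and SAP 3.6.1.2, 3.6.1.3, 3.6.2.2 and 3.6.2.3:

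1. Define the FAS for each device as all randomised, trained subjects who attempt at least one self-injection with the assigned device, whatever amount is delivered.
2. Score an attempt with no delivery, partial delivery or, for the 1mL devices, a single injection as not safe and effective at that visit. State that this applies to the subject's own failed attempt even where SAP 11.1 would otherwise drop the assessment because someone else then injected.
3. Define the Safety Set as all subjects with at least one attempted use of the device, whatever amount is delivered.
4. List the change in SAP 3.10, which already widens the FAS by keeping subjects with important protocol deviations.

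Do not score visits missed for device-unrelated reasons, such as the COVID-19 disruptions in SAP 5.3, as failures in the main analysis. That would answer a different question; show it as a sensitivity analysis.

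**Cost.** Wording and programming. The CRF must also identify attempts that delivered nothing, and the documents do not describe such a field, so this needs checking. The Baseline percentages can only stay the same or fall.
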